## Study Design

Describe and explain the study design (e.g., observational, secondary analysis, single/double blind, parallel, crossover, deception, etc.).

- *Clinical Research:* Indicate whether subjects will be randomized and whether subjects will receive any placebo.
- *Community-Based Participatory Research:* If you are conducting [community-based participatory research \(CBPR\)](#), describe strategies for involvement of community members in the design and implementation of the study, and dissemination of results from the study.
- *Qualitative research:* Indicate ranges where flexibility is needed, if a fixed interview transcript is not available, describe interview topics including the most sensitive potential questions.

- **Research Repositories:** If the purpose of this submission is to establish a Research Repository (bank, registry) and the material you plan to collect is already available from a commercial supplier, clinical lab, or established IRB approved research repository, provide scientific justification for establishing an additional repository collecting duplicate material. Describe the repository design and operating procedures. For relevant information to include, see the [UK Research Biospecimen Bank Guidance](#) or the [UK Research Registry Guidance](#).

In this 3 x 2 design, patient participants (N = 150) will be randomly assigned to receive treatment modules sequenced according to the following three module-ordering conditions: 1) Standard: In accordance with the standard, published UP manual; 2) Capitalization: organized to prioritize skills that capitalize on patient strengths; 3) Compensation: organized to prioritize skills that compensate for patient weakness. All participants will also be randomized to two treatment-duration conditions: 1) Brief: 7 sessions; or 2) Full: 13 sessions. Deception will not be used – patients will be fully informed about the possibility of being assigned to the Brief or Full treatment length condition. However, during the consent process, we have elected to limit the information provided about each ordering scheme. Instead, participants will be told that we may use their self-report questionnaire data to determine the order of their skills. This omission of information is justified for the following reasons: 1) knowing their condition may bias results and, given that the conditions are face valid, patients may be able to guess their assignment if they are provided detailed information about the possibilities, and; 2) although research provision of manualized interventions (like the UP) are typically delivered in a standard order, it is common in routine practice for therapists to make decisions about how to order treatment skills without providing patients with reasoning. Following the final assessment, patients will be provided with information about the three module-ordering conditions and the condition to which they had been assigned will be revealed.

Clinician participants will not be randomized - all clinicians will be asked to attend a training workshop in the Unified Protocol and participate in weekly consultation calls with [name] or [name]. They will provide care in each patient condition (standard, capitalization, compensation; brief, full). Clinicians will be asked to complete surveys and interviews about their impressions participating in this study/providing care based patient strengths/weaknesses.

## Attachments

### Subject Recruitment Methods & Advertising

Describe how the study team will identify and recruit subjects. Please consider the following items and provide additional information as needed so that the IRB can follow each step of the recruitment process.

- How will the study team identify potential participants?
- Who will first contact the potential subjects, and how?
- Will you use advertisements? If so, how will you distribute those?
- How and where will the research team meet with potential participants?
- If applicable, describe proposed outreach programs for recruiting women, minorities, or disparate populations.
- How you will minimize undue influence in recruitment?
- Attach copies of all recruiting and advertising materials (emails, verbal scripts, flyers, posts, messages, etc.).

For additional information on recruiting and advertising:

- [IRB Application Instructions - Advertisements](#)
- [PI Guide to Identification and Recruitment of Human Subjects for Research](#)

As of December 21, 2020, no participants have been enrolled, recruited, or completed any study procedures.

Patient participants will be recruited from the pool of individuals seeking treatment at UK Psychiatry's Outpatient Clinic. During their intake appointment for non-research services at UK Psychiatry, participants will be asked to provide their consent to be contacted by research teams to learn more about ongoing research studies. A member of our study team will attend weekly staffing meetings at UK Psychiatry, where intakes from the previous week are discussed. Study staff may overhear PHI for people not involved in the study in the course of these meetings. We will work to mitigate these occurrences by having study staff only attend portions of these meetings when new potential patients are being introduced. Even so, study staff still may overhear PHI regarding potential participants who do not ultimately meet study criteria. This process will be designed to minimize the amount of non-study-related PHI study staff may overhear. Study staff will obtain observer privileges from UK Healthcare in order to attend these meetings. Patients that likely meet study criteria (who gave their consent to be contacted by ongoing research studies) will be contacted by our study team to conduct a phone screen (see attached). Residents will provide study staff with the names, phone number(s), and email address(es) of potential participants so study staff do not have to access participants' and potential participants' medical records.

With regard to clinician participants, UK Psychiatry currently employs 10 clinicians who meet study inclusion criteria. Leadership at UK Psychiatry (i.e., Department Chair, VP of Research, Director of Outpatient Services) are invested in successful completion of this study and have assessed clinician interest in being a part of this effort (see attached letter of support). To recruit clinician participants, we will ask the Director of Outpatient Services at UK Psychiatry to send an informational email about the study to UK psychiatry clinicians; those with interest in participating will be asked to contact study staff directly (see attached email template).

We will recruit directly from the patient/clinician pool at UK Psychiatry. In line with current standard practice, residents and supervisors within the UK Psychiatry department will ask patients and potential patients if they are interested in being contacted to participate in research studies. No further advertising will be conducted.

## Attachments

## Research Procedures

Describe how the research will be conducted.

- What experience will study participants have?
- What will study participants be expected to do?
- How long will the study last?
- Outline the schedule and timing of study procedures.
- Provide visit-by-visit listing of all procedures that will take place.
- Identify all procedures that will be carried out with each group of participants.
- Describe deception and debrief procedures if deception is involved.

Upon referral to the study via the recruitment methods described above, patient participants will complete a brief telephone screening (see attached). The screen will predominantly be conducted by trained undergraduate/post-baccalaureate research assistants, however the PI or a supervised graduate students/post-doctoral scholars may also conduct the phone screens. Screening forms for individuals who are deemed to be ineligible for the study will be shredded.

Likely eligible participants, determined by the phone screen, will be invited to attend an in-person session at UK Psychiatry or a virtual session using either UKHealthCare HIPAA-compliant Zoom or phone (Assessment Visit 1). As described above (see "Informed Consent" section), a study assessor (i.e., doctoral students in clinical psychology/post-doctoral scholar) will review study procedures with potential participants and ask them to provide their informed consent. After informed consent is provided, an interview-based diagnostic assessment will be administered in order to confirm clinical inclusion/exclusion criteria, as well as to provide a baseline level of clinical severity. This assessment visit will be audio-recorded provided participants give their consent for this. Next, patients will be asked to complete a battery of self-report questionnaires, which will assess symptoms of anxiety/depression, level of functioning (i.e., clinical interference, quality of life), and proficiency in the skills taught during treatment with the UP. Those that are deemed ineligible after this assessment will be withdrawn, whereas we will work with eligible participants to schedule their next study session (Treatment Session 1). After Assessment Visit 1, study staff (i.e., research assistant) will randomly assign them to one of three module-ordering conditions: Standard (modules order according to the published manual), Capitalization (modules ordered to prioritize patient strengths) and Compensation (modules ordered to prioritize patient weaknesses). The completed self-report battery from Assessment Visit 1 will be used to order modules for those assigned to the Capitalization and Compensation conditions. Study therapists (i.e., clinicians at UK psychiatry), study assessors (i.e., doctoral students in clinical psychology/post-doctoral scholar), and participants will be blind to module-ordering condition.

Following Assessment Visit 1, all participants will begin completing weekly treatment sessions in person, via phone, or via HIPAA-compliant video conferencing service (i.e., Zoom via the UK HealthCare portal); the order of treatment skills will be determined based on their assignment to module-ordering condition. Before the start of Treatment Session 5, clinician participants will alert study staff (i.e., research assistant) to request a randomization to a Treatment Length Condition: Brief (6 sessions) or Full (12 sessions). Treatment Length Randomization will occur at this stage to limit expectancy effects on therapists' and participants' behaviors, while also allowing therapists and participants to plan their final 2 sessions together with this randomization in mind. Participants randomized to the Brief treatment condition be reminded during Treatment Session 6 how they can use the skills learned in the previous sessions in the upcoming weeks to prevent relapse. In the event that participants are at an imminent risk of harm to themselves or others at this session, the therapist will work with the PI to develop a safety plan with the participant which may include referrals to other psychotherapy resources or hospitalization.

We will use a treatment window during which the assigned number of sessions will be completed; specifically, patients randomized to the Brief condition will complete 7 sessions during an 10-week window and patients randomized to the Full condition will complete 13 sessions during a 20-week window. This will allow us to account for scheduling challenges (e.g., patient/therapist illness, vacation). The first session for all participants will be an "orientation to treatment" session in which presenting concerns will be reviewed and an overview of the treatment model will be provided. As noted previously, the skills delivered during the remaining sessions in this study will be drawn from the UP. Four of the five UP modules will be implemented 2 sessions: Understanding Emotions, Mindful Emotion Awareness, Cognitive Flexibility, and Increasing Interoceptive Tolerance. The 5th UP module, Countering Emotional Behaviors, is designed to be implemented in 4 sessions. All sessions will last for 60 minutes in duration. Thus, depending on treatment length and module order, each participant will receive 2 to 5 UP modules during this study. It is important to note that the therapeutic strategies involved in all modules are all common, evidence-based cognitive-behavioral strategies and are not, themselves, under study; instead, we are interested in whether personalized sequencing leads to faster improvements (not whether patients improve at all - we expect that most will improve). Every module involves reading from a published manual (the Unified Protocol for the Transdiagnostic Treatment of Emotional Disorders; Barlow et al., 2018) and completing homework assignments outside of the treatment session (this intervention has previously been reviewed by UK's non-medical IRB). These treatment sessions will be audio-recorded provided participants give their consent for this; this will allow study staff to rate sessions for fidelity to the protocol.

Regardless of randomization, all participants will be scheduled for Assessment Visit 2 to occur between treatment sessions 5 and 6. Participants will complete an interview-based diagnostic assessment with a study assessor that will focus on the diagnoses assigned at Assessment Visit 1. This assessment may take place in person at UK psychiatry, over the phone, or via HIPAA-compliant Zoom. This assessment visit will be audio-recorded. Participants will also complete the same battery of self-report questionnaires at this visit as at Assessment Visit 1. All participants will also complete Assessment Visit 3, which will take place between weeks 13-16 (corresponding to the end of the treatment window for the Full length condition). This assessment visit will also be audio-recorded and may take place in person at UK Psychiatry, over the phone, or via HIPAA-compliant Zoom. Finally, Assessment Visit 4 will take place (in person at UK Psychiatry, over the phone, or via HIPAA-compliant Zoom) between 46 and 50 weeks after Assessment 1 and will include the same questionnaires.

Following the last treatment session (Treatment Session 13 for participants in the Full treatment condition; Treatment Session 7 for participants in the Brief treatment condition), participants will be asked to provide satisfaction ratings and written qualitative feedback on their experience with the treatment they received. Additionally, all participants will be asked to complete a weekly self-report battery assessing symptoms, skill proficiency, and skill knowledge for 20 weeks (again corresponding to the treatment window for the Full length condition); patients in the Brief condition will continue to complete these questionnaires after discontinuing treatment. These questionnaires will be emailed to participants and we will ask that they are completed within two days of receipt.

All self-report questionnaires will be completed online via REDCap. This survey platform is designed specifically for collection of research data, and therefore meets the privacy standards imposed on health care records by the Health Insurance Portability and Accountability Act (HIPAA). For Assessment Visits (1-4) that take place at UK psychiatry, self-report batteries will be completed on-site using a study iPad. The battery administered weekly between treatment sessions, along with the Assessment visits that take place remotely, will be emailed to participants to be completed on their own devices. Finally, although we anticipate that most patients will prefer to complete these measure electronically, we can provide paper and pencil versions of the questionnaires if requested.

There may be circumstances in which study patients are referred for additional care (i.e., they finish all study procedures and request a referral, they are withdrawn due to deterioration and given referrals to immediate treatment). No written information from the official study record (i.e., self-report questionnaire scores, assessor ratings) would be shared with UKHealthcare, or any other outside provider, upon referral after study. However, to streamline care, we will instruct the patient to ask their new provider to serve the study with a medical release of information (signed by the new provider and the patient) that allows their study clinician to speak with their new provider and provide clinical impressions. The release of information is a standard form for medical practitioners in routine care; since this is a not a study document, we have not attached it here.

Clinician Participants will be asked to attend a one-day training workshop on the Unified Protocol. The PI, [name], was the founding director of the Unified Protocol Institute in her previous academic position at Boston University; in this role, she routinely provided this training, which will consist of didactic lecture and role plays. After the workshop, clinicians will be asked to begin implementing the UP with patients on their caseload that have consented to participate in this study. Clinicians will also attend weekly consultation calls with the PI who will provide additional guidance on the delivery of the study intervention; clinicians will be asked to participate in these calls for the duration of time they have study patients on their caseload. Clinicians will be asked to audio-record their work delivering the UP with their study patients; these tapes will be rated for adherence and competence with the protocol (see attached adherence checklists that study staff will use to rate tapes). Study staff will provide clinicians these audio-recorders for the duration of the study; study staff will stop by clinicians' offices to pull recordings off the audio recorder and upload them directly to the UK provided, password-protected TIPS lab server space. Finally, clinicians will be asked to fill out questionnaires at several time points during the study: 1) directly following provision of their informed consent, 2) following completion of the didactic workshop, and 3) after all patient treatment has been completed. Following their provision of informed consent, all questionnaires will be collected via an email with a link to an online REDCap survey.

To assess clinician and patient perspectives on the study design and treatment provided, trained study staff will conduct semi-structured individual qualitative interviews and small focus groups with clinicians (at the conclusion of their final study treatment case) and patients (at week 20). These qualitative interviews will be conducted by study staff members at Suffolk University who have been added as study personnel. These staff members have obtained guest LinkBlue IDs that allow them to access HIPAA-compliant UK resources to conduct research procedures involved in this study. The Suffolk University site will oversee the qualitative component of this protocol (see Reliance Agreement, submitted with this modification request). UK IRB-approved Suffolk University-based study staff will conduct the qualitative interviews remotely (by phone calls or Zoom via the UK HealthCare portal), transcribe the interview recordings, and code the transcriptions. All recordings, transcriptions, and coding files will be saved on the approved UK server. Suffolk University-based study staff have created guest LinkBlue IDs and have submitted the necessary paperwork through UK's IT department to be granted access by the PI to this server. Suffolk University-based study staff will also have access to UK HealthCare's HIPAA-compliant Zoom portal to ensure the confidentiality of communications with participants.

Post-treatment qualitative interviews, lasting 30 min, will be conducted with participants. Qualitative interviewers will use an interview guide designed to gather information on participant experience and perceived acceptability of the study and the personalized treatment more broadly at first, narrowing to a focus on specific questions of interest (e.g., experience with second stage randomization, patient treatment values and preferences, desire for more collaborative approaches to treatment planning, patient-identified points of confusion understanding capitalization vs compensation approaches). The outlines of the clinician and patient interview guides, with the primary topic areas and questions, are included in the Data Collection section. These guides will be refined as interviews continue, in response to participant feedback (e.g., clarifying questions participants find confusing, including questions to collect more information on topics that previous participants have raised). The process of iteratively refining interview questions in response to participant feedback is a common and necessary practice in qualitative research, as participants provide researchers with new insights they had not previously considered. Modifications to the interview guide (e.g., including questions about a completely new topic) will be submitted to the UK IRB for review. Interviews, averaging 30 minutes, will use established procedures described in detail by Gilchrist (1992), and will be audio-recorded and transcribed. At the conclusion of the study, two focus groups, lasting 1 hour each, with clinicians (4-6 clinicians each) and two focus groups with patients (4-6 patients each) will be used as a form of "member checking" to both validate through triangulation the researchers' interpretations of the information obtained from the semi-structured interviews and to identify through expansion any additional information or insights as to clinician and patient perspectives on the study and treatment. Predetermined probes will be used to keep the discussion on track, following a funnel structure beginning with broader researcher-driven issues and narrowing to more participant-driven illustrations of the issues (Morgan, 1988).

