With regard to clinician participants, those that express interest in participating following receipt of the email invitation will be scheduled for individual informed consent visits at UK psychiatry. Study staff (i.e., doctoral students in clinical psychology/post-doctoral scholars) will explain study procedures. The clinician participants will be given a chance to read the informed consent document and ask any questions. Similarly, these informed consent documents may be hard copies or electronic copies stored in REDCap. Electronic copies with participants' electronic initials and signatures will be stored separately from participants' data. Patients will be encouraged to discuss any issues that arise with their study assessor (not their therapist, who is not study staff). However, if they do not feel comfortable expressing concerns with this person, they are encouraged to reach out the PI via the contact information on the consent form. The PI will make every effort to address these concerns, if necessary, following up with appropriate study staff (without identifying the particular patient) and implementing procedural changes. We will also provide ORI's contact information for participants in the event that they would have complaints or concerns. Clinicians participants will be encouraged to reach out to the PI directly with concerns and will also be provided ORI's contact information.

Request for Waiver of Informed Consent Process

If you are requesting IRB approval to waive the requirement for the informed consent process, or to alter some or all of the elements of informed consent, complete, Section 1 and Section 2 below.

Note: The IRB does not approve waiver or alteration of the consent process for greater than minimal risk research, except for planned emergency/acute care research as provided under FDA regulations. Contact ORI for regulations that apply to

single emergency use waiver or acute care research waiver [contact]).

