**Pilot Test of Personalization Aims (ordering and discontinuation).** In addition to our primary aim of establishing the feasibility/acceptability of our personalization strategies and study design, we seek to determine whether a preliminary signal exists to support the notion that personalized sequencing and target-informed discontinuation can enhance treatment efficiency. First, to explore whether personalized sequencing leads to more efficient improvements in the core process addressed by the UP, we will use hierarchical linear mixed modeling (HLMM) to compare the average rate of change in clinical outcomes among the three UP sequencing conditions (UPS, UPP-CA, and UPP-CO). The primary outcome measure for aim is the distress aversion subscale from the MEAQ (MEAQ-DA), which has previously been used to demonstrate target engagement with the UP (see Preliminary Studies). Additionally, to examine whether core process engagement can serve as an early indicator of treatment response, prompting discontinuation, we will assess variability in MEAQ-DA levels at the second stage randomization (S5 assessment), along with the degree to which any patients randomized to discontinue demonstrate additional symptom improvement (using HAM-A ratings) in the absence of treatment such that they are responders by the W20 assessment. We will also explore whether patterns exist between S5 MEAQ-DA scores and responder status for those that discontinued after session 6.

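### The plan masks assessors to module order but states no masking to treatment length, leaving the HAM-A results after discontinuation open to rater expectancy

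*Combined protocol and SAP*

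**What the plan says.** The masking statement is in Research Procedures, in the paragraph on Assessment Visit 1: "study assessors (i.e., doctoral students in clinical psychology/post-doctoral scholar), and participants will be blind to module-ordering condition". Study therapists are named in the same sentence. It covers module order and nothing else.

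For the second factor, treatment length, the same section offers one safeguard: "Treatment Length Randomization will occur at this stage to limit expectancy effects on therapists' and participants' behaviors". Assessors are not mentioned.

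On timing, Research Procedures says "Before the start of Treatment Session 5, clinician participants will alert study staff" to request the length allocation, and that "all participants will be scheduled for Assessment Visit 2 to occur between treatment sessions 5 and 6". At that visit, "Participants will complete an interview-based diagnostic assessment with a study assessor".

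The Informed Consent Process section gives the route for patient concerns: "Patients will be encouraged to discuss any issues that arise with their study assessor", with the PI as the alternative for a patient who is uncomfortable with that.

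The Statistical Design section (pilot test of the personalization aims) asks how far patients randomized to discontinue show "additional symptom improvement (using HAM-A ratings) in the absence of treatment", so that they count as responders by the W20 assessment. It also looks for a pattern between their session-5 MEAQ-DA scores and responder status.

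**The concern.** The plan recognises expectancy as a threat to the treatment-length factor and delays randomization for that reason. It then leaves the outcome rater out of the protection. HAM-A is the outcome named for the discontinuation question, and it calls for judgement. A rater who knows that a patient's treatment has stopped knows the exposure under study. That rater might score residual anxiety more severely, expecting relapse, or more leniently, expecting brief treatment to be enough.

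At stake is the preliminary signal on discontinuation. The Power Analyses section says the pilot's effect sizes and variability will be used to decide whether further testing is warranted. A responder proportion among discontinued patients that partly reflects rater expectation would mislead that decision.

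**Working it through.** The plan states no figure on this point, so the check sets the sections side by side.

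**1. Scope of masking.** Research Procedures masks therapists, assessors and participants to order. No section masks anyone to length. Therapists request the length allocation and plan the closing sessions with the patient, so both know it.

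**2. Timing.** Length is randomized before Session 5. Visit 2 falls between Sessions 5 and 6, and Visits 3 and 4 come later. All three post-baseline visits therefore follow allocation; only Visit 1 precedes it.

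**3. Who rates HAM-A.** No rater is named. The Data Collection section lists HAM-A under Assessment Visits and not in the weekly battery. Assessors conduct the Visit 2 interview. Research Procedures separates "self-report questionnaire scores, assessor ratings" in describing the study record, and the Records, Privacy, and Confidentiality section lists clinician-rated interview data. Assessor rating is a reasonable inference, not a stated fact.

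**4. Routes by which length can reach the rater.**
- Patients are pointed to the assessor with issues. The Risks section names ending treatment before remission as the main risk of the Brief condition, so early stopping is a foreseeable issue to raise.
- The Resources section gives the same post-doctoral scholar and doctoral students two jobs: assessing patients and supporting the clinicians.
- The risk-minimization list has the PI meeting weekly with research staff and clinicians together.
- A Concurrent Treatment Form is collected at Visits 2 to 4. Who administers it is not stated.

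**5. Results exposed.** These are HAM-A improvement and responder status among discontinued patients, and the pattern of responder status with session-5 MEAQ-DA. A constant rating shift would cancel in a change score taken between two post-allocation visits. It would not cancel in change from Visit 1, nor where responder status depends on the level reached. The plan does not define a responder, so the applicable case is unknown. The sequencing comparison uses MEAQ-DA, a questionnaire subscale, and is not touched.

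**6. Size, illustration only.** The documents give no HAM-A SD, responder rate or responder rule. Assume a normal HAM-A score with SD 7, a single cut-off giving 50% responders, and a rating shift of d points. The responder rate becomes Φ(d/7) for lenient rating and Φ(−d/7) for severe rating.

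| Shift d | d/7 | Lenient | Severe |
|---|---|---|---|
| 1 | 0.143 | 55.7% | 44.3% |
| 2 | 0.286 | 61.2% | 38.8% |

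That is about 6 to 11 percentage points in either direction. A percent-change or composite responder rule would give other numbers.

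**7. Related inconsistencies.** Statistical Design places responder status at W20. Research Procedures puts Visit 3 at weeks 13 to 16, and the weekly battery, which runs to week 20, contains no HAM-A. The Brief condition has 6 sessions in one part of Research Procedures and in Statistical Design, but 7 in Study Design and elsewhere in Research Procedures. These passages must be reconciled before one can say which rating counts as post-discontinuation.

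**The case against.** The strongest reply is that the planned HAM-A analysis is not a comparison by length. It describes patients who were all randomized to discontinue. The usual harm, different rating in two arms that are then compared, does not arise in any analysis the plan specifies. This stands. What remains is a possible shift in one group's proportion and in its pattern with MEAQ-DA, plus exposure of any Brief-versus-Full contrast added later.

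The trial is also a pilot whose primary aim is feasibility and acceptability, which limits the consequence. The routing of concerns sits in the consent section and makes disclosure of length likely without proving it.

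A reader might infer that the plan declares assessors unblinded to length. It does not; it is silent. A reader might also infer that the bias could never be examined. Research Procedures says Visits 2 and 3 are audio-recorded, so masked re-scoring is a partial check, although recordings may themselves reveal length.

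Finally, the Subject Info To-Date section shows 50 enrolled and none newly reported, so wording changes may reach few remaining visits. That affects which part of the fix is useful, not whether the gap exists.

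**Conclusion.** The point holds as an omission made worse by the plan's own arrangements. No masking of assessors to treatment length is stated, every post-baseline HAM-A visit follows length allocation, and the plan's routing of concerns and its dual staff roles work against masking. The HAM-A results among discontinued patients, and any later comparison by length, are open to rater expectancy of unknown size and direction.

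This rests on two inferences: that assessors rate HAM-A, and that they would commonly learn the length. The 6 to 11 point range is an illustration under assumed inputs, not an estimate.

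The documents do not support extending the concern to the trial's main efficacy comparison. The module-order analysis of MEAQ-DA is unaffected. The point deserves correction in proportion to a secondary aim of a pilot.

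**What to change.** - **Research Procedures, masking sentence:** state that HAM-A raters are masked to treatment length at all post-baseline visits where HAM-A is given (2 to 4), and name who rates it.
- **Visit script:** add a line asking patients not to disclose their assigned length or treatment status to the rater. Collect the Concurrent Treatment Form by self-report or after the HAM-A. The plan's safety procedures stay as they are.
- **Informed Consent Process:** make the PI or a research assistant the first contact for concerns. Both roles already exist.
- **Staff roles:** keep raters out of clinician support and case discussions for patients they rate.
- **Record:** log any unblinding, with visit and source.
- **Visits already completed:** have existing staff who are unaware of length re-score a sample of the audio recordings where feasible, and report the masking status as a limitation.
- **Separately:** reconcile the W20 HAM-A with the timing of Visit 3, and the 6- and 7-session descriptions of the Brief condition.

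The cost is mainly wording, a script line and a log. Separating roles takes some scheduling in a small team, and re-scoring takes staff hours. Some accidental unblinding will remain, and recordings may contain cues.
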